#### **10.4.4 Other safety variable(s)**

##### **10.4.4.1 Physical Examination**

Data from the Physical Examination are only provided in subject data listings presented by treatment group, subject and visit, displaying all data collected for all subjects. No summaries will be provided. Findings that are considered clinically significant will be reported AEs.

#### 10.4.4.2 Neurologic Examination Data

Data from the Neurological Examination are collected on the Neurological Examination Complete and Neurological Examination Brief CRFs and are not summarized. Data from the Neurological Examination are only provided in subject data listings presented by treatment group, subject and visit, displaying all data collected for all subjects. No summaries will be provided. Findings that are considered clinically significant will be reported as AEs.

#### 10.4.4.3 Psychiatric and Mental Status Data

The Psychiatric and Mental Status assessment is performed at Baseline and all scheduled visits. These data are collected on the Psychiatric and Mental Status CRF. Assessment of specific domains of psychiatric and cognitive symptoms will be performed by a staff member trained in the identification of psychiatric symptoms. The parameters that evaluated are orientation, attention, memory, mood, and calculus. These parameters will be assessed as normal or abnormal and then determined whether clinically significant. The presence of psychiatric symptoms, mental impairment, or behavioral problems are also assessed and evaluated as normal or abnormal, and whether they are clinically significant.

For each of these assessments, the number and percentage of subjects with an abnormal result, and the number and percentage with an abnormal result considered clinically significant, will be summarized at each scheduled visit.

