10. For subjects developing psychiatric/mood/behavioral signs or disturbances (see examples in list below) that are clinically concerning or that worsen over time, the subject should be referred immediately to a mental healthcare professional and must be withdrawn from the study.
 - Auditory or visual hallucinations
 - Delusions/paranoia/grandeur
 - Disorganized thought process
 - Agitation/aggression/apathy
 - Dysphoria/depression/mood lability/euphoria
 - Disinhibition
 - Cognitive changes/memory impairment/delirium
 - Aberrant motor behavior
11. Subject is suspected of having a serious multiorgan hypersensitivity reaction. Serious suspected multiorgan hypersensitivity cases may be identified and reported to the Sponsor by the Investigator using the following algorithm:
 - An AE or laboratory value (as defined below) suggestive of internal organ involvement including but not limited to hepatitis, nephritis, pneumonitis, carditis, colitis, encephalitis,

pancreatitis, myositis, arthritis, or hematologic system involvement) combined with at least 1 of the following: fever, rash, lymphadenopathy, or eosinophilia

- Treatment-emergent abnormal laboratory value criteria suggestive of internal organ involvement or eosinophilia:
- Eosinophils percentage $\geq 10\%$
- Eosinophils absolute $\geq 0.5\text{G/L}$
- Neutrophils absolute $< 1.5\text{G/L}$
- Platelets absolute $\leq 100\text{G/L}$

12. There is confirmation of a pregnancy during the study, as evidenced by a positive pregnancy test.

Investigators should attempt to obtain information on subjects in the case of withdrawal or discontinuation. For subjects considered as lost to follow up, the Investigator should make an effort (at least 1 phone call and 1 written message to the subject), and document his/her effort (date and summary of the phone call and copy of the written message in the source documents), to complete the final evaluation. All results of these evaluations and observations, together with a narrative description of the reason(s) for removing the subject, must be recorded in the source documents. The eCRF must document the primary reason for withdrawal or discontinuation.

Investigators should contact the Medical Monitor, whenever possible, to discuss the withdrawal of a subject in advance.

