### **2.4.2 Other safety variables**

Other safety variables are as follows:

- Incidence of TEAEs reported by the subject and/or caregiver or observed by the Investigator during the following periods: 16-week Treatment Period, 12-week Maintenance Period, 4-week Titration/Stabilization Period, and 3-week Taper Period
- Number of and reason for subjects requiring premature tapering due to TEAEs
- Number of and reason for subjects requiring a dose reduction during the Stabilization Period due to TEAEs
- Incidence of treatment-emergent SAEs during the following periods: 16-week Treatment Period, 12-week Maintenance Period, 4-week Titration/Stabilization Period
- Changes in clinical laboratory test parameters (including hematology, blood chemistry, and urinalysis)
- Changes in vital sign parameters (including pulse rate, systolic BP, diastolic BP, and respiratory rate)
- Changes in 12-lead ECG parameters
- Physical examination (including body weight) and neurological examination findings

- Changes in Psychiatric and Mental Status
- Occurrence of valvular abnormalities or pericardial effusion changes or other significant abnormalities as identified by 2-dimensional Doppler echocardiogram at each assessment by central reader
- Changes in withdrawal symptoms using Clinical Institute Withdrawal Assessment-Benzodiazepines (CIWA-B) from the End of Treatment Visit (Visit 7) to end of the Taper Period (Visit 8) and end of the SFU Period (Visit 9 [30 days after the last IMP intake]).

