## 3 DATA ANALYSIS CONSIDERATIONS

### 3.1 General presentation of summaries and analyses

Statistical analysis and generation of tables, figures, subject data listings, and statistical output will be performed using SAS Version 9.3 or higher. All tables and listings will use Courier New font size 9.

Descriptive statistics will be displayed to provide an overview of the study results. For categorical variables, the number and percentage of subjects in each category will be presented. Unless otherwise noted, all percentages will be displayed to 1 decimal place. No percentage will be displayed for zero counts, and no decimal will be presented when the percentage is 100%. For continuous variables, descriptive statistics will include number of subjects with available measurements (n), mean, SD, median, minimum, and maximum.

Decimal places for descriptive statistics will always apply the following rules:

- “n” will be an integer
- Mean, SD, and median will use one additional decimal place compared to the original data
- Minimum and maximum will have the same number of decimal places as the original value.

Unless otherwise specified, statistical tests of efficacy variables will be presented as two-sided p values rounded to three decimal places. P-values less than 0.001 will be presented as “<0.001” and p-values greater than 0.999 will be presented as “>0.999.” Statistical comparisons will be two-sided and will be performed at the 0.05 level of significance.

A complete set of data listings containing all documented data as well as calculated data (e.g., change from Baseline), as applicable, will be generated.

Treatment groups will be displayed as: Placebo, PSL 50 mg bid, PSL 100mg bid, PSL 200mg bid, and PSL 400mg bid.

Log-transformation is based on natural logarithm. For analyses on log-transformed values, model estimates will be back-transformed to anti-log space for table presentation. See Section 8.1.1 for details.

Data collected at scheduled visits will be included the by-visit summary. Data collected at unscheduled visits will not be included in the by-visit summary, but will be considered when determining the Last Visit, minimum, and maximum post-Baseline values during the Treatment Period. Data collected on Visit 8 will be summarized separately for subjects in the Conversion Period versus the Taper and Safety FU Period.

In general, all CRF data will be presented in the subject listings.

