### **3.2.2.2 End of the 16-week treatment period**

The end of the 16-week overall treatment period will be either the date of Visit 7 for subjects completing the Treatment Period, or the date of the early discontinuation visit (EDV), for subjects who discontinued during the Treatment Period. If a subject does not have a Visit 7/EDV, then the date of the final contact will define the end date of the Treatment Period.

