### **3.2.4 Mapping of assessments performed at early discontinuation**

Unlike other scheduled visits, an early discontinuation visit (EDV) doesn't have a predetermined visit window and can occur at any days during the study. If an EDV occurs at the day of a scheduled visit, assessments (in-clinic safety assessments such as vital signs, ECGs, and blood collection for clinical laboratory assessments) should correspond to that scheduled visit. Assessments at an EDV that occurs on a day between two scheduled visits will be assigned to the next scheduled visit. All other assessments (such as questionnaire and PK samples) collected on an EDV will not be mapped.

In the by-visit summary tables, only nominal (scheduled) visits where the assessment is scheduled will be included. For example, if a subject had an EDV after Visit 4 and before Visit 5, the applicable assessments will be mapped to Visit 5 (ie, the next scheduled visit). Vital signs and ECGs collected at the EDV will be summarized under Visit 5 in the by-visit summary tables. However, Visit 5 will not be included in the by-visit summary tables for the clinical laboratory assessments as lab assessments are not scheduled on Visit 5. Unscheduled visits will not be mapped to scheduled visits. In the subject listing, data will be presented under the actual visits, including EDV and unscheduled visits.

Seizure data collected by diary are associated with periods defined within the study and as such need no mapping to visits. If a subject withdraws between visits an effort is made to recover all diary records for use in calculation of seizure frequencies.

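### The SAP tabulates how many subjects are abnormal on Psychiatric and Mental Status at each visit, but no table of this assessment shows who became abnormal or worsened after Baseline

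*SAP*

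**What the plan says.** **The variable.** Protocol 4.2.2 and SAP 2.4.2 list "Changes in Psychiatric and Mental Status" among the other safety variables.

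**The planned table.** For each item of the assessment, SAP 10.4.4.3 gives "the number and percentage of subjects with an abnormal result, and the number and percentage with an abnormal result considered clinically significant", and these "will be summarized at each scheduled visit". The section has no shift from Baseline, no treatment-emergent category and no count of subjects abnormal at any time on treatment.

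**Unscheduled visits.** SAP 3.1 states: "Data collected at unscheduled visits will not be included in the by-visit summary". The same sentence goes on to say that such data do count towards the Last Visit and the post-Baseline minimum and maximum. SAP 3.2.5 adds a Last Visit row to by-visit summaries by default and defines it as the last non-missing assessment in the Treatment Period, scheduled or unscheduled.

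**Early discontinuation.** Under SAP 3.2.2.2 the Treatment Period ends on "the date of the early discontinuation visit (EDV), for subjects who discontinued during the Treatment Period". SAP 3.2.4 has two rules. For in-clinic safety assessments, with vital signs, ECG and laboratory samples as examples: "Assessments at an EDV that occurs on a day between two scheduled visits will be assigned to the next scheduled visit". For the rest: "All other assessments (such as questionnaire and PK samples) collected on an EDV will not be mapped". Psychiatric and Mental Status is named in neither group.

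**Withdrawal.** Under Protocol 6.3, criterion 10, for psychiatric, mood or behavioral disturbances that are clinically concerning or that worsen, "the subject should be referred immediately to a mental healthcare professional and must be withdrawn from the study".

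**The concern.** A change variable needs each subject's on-treatment result set against that subject's own Baseline. A visit percentage combines subjects who were already abnormal at Visit 2 with those who became abnormal later, and it loses both those who recovered and those who left.

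The program has a reason to look closely here. Protocol 2.3.1 reports acute, transient psychiatric effects that required psychiatric admission in 3 subjects given padsevonil. Protocol 11.3.7 calls for close monitoring of this status, and Protocol 13.7 singles out behavioral events for the Data Monitoring Committee. At stake is whether the structured assessment made at every clinic visit from Visit 2 can show, by arm, how many subjects developed a new or worse abnormality.

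**Working it through.** The documents state no figure for this summary, so there is nothing to reproduce. The check sets the safety sections side by side and then works one illustration.

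**Comparison with the other safety data**

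| Data | Planned comparison with Baseline | Planned any-time or worst-value count |
|---|---|---|
| Laboratory (SAP 10.3) | Change from Baseline; shift to maximum and minimum (hematology and chemistry) | Possibly clinically significant values at any time, unscheduled visits included |
| Vital signs (SAP 10.4.1) | Change from Baseline | Subjects meeting abnormality criteria in the Treatment Period |
| ECG (SAP 10.4.2) | Change from Baseline | Subjects meeting abnormality criteria in the Treatment Period |
| Psychiatric and Mental Status (SAP 10.4.4.3) | None | None |

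**Which results reach a table**

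1. A result at a scheduled visit enters that visit's row.
2. A result at an EDV enters the Last Visit row, because the EDV ends the Treatment Period. Whether it also enters a visit row depends on the mapping that SAP 3.2.4 leaves open.
3. A result at an unscheduled visit enters only the Last Visit row, and only if it is the last one. An abnormality that resolves before the last assessment is in no table.
4. No row shows the subject's own Baseline status. A Baseline row allows a comparison of group percentages only.

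**Illustration**

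The arm size of 80 is from SAP 2.7. Every other count is assumed. Let 16 of 80 subjects (20.0%) be abnormal at Baseline and stay so. Let 8 further subjects become abnormal, 2 of them found at an EDV falling before each of Visits 3, 4, 5 and 6, and then leave the study.

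| Row | EDV mapped | EDV not mapped |
|---|---|---|
| Visit 3 | 18/80 = 22.5% | 16/78 = 20.5% |
| Visit 4 | 18/78 = 23.1% | 16/76 = 21.1% |
| Visit 5 | 18/76 = 23.7% | 16/74 = 21.6% |
| Visit 6 | 18/74 = 24.3% | 16/72 = 22.2% |
| Visit 7 | 16/72 = 22.2% | 16/72 = 22.2% |
| Last Visit | 24/80 = 30.0% | 24/80 = 30.0% |

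- With mapping, no visit row is more than 24.3 − 20.0 = 4.3 points above Baseline. Without it, the 8 new cases are in no on-treatment visit row.
- The Last Visit row holds all 8 but does not tell them apart from the 16.
- A new-onset count gives 8/(80 − 16) = 8/64 = 12.5%. If the assumed Baseline rate is 0%, 10%, 20% or 40%, it gives 8/80 = 10.0%, 8/72 = 11.1%, 8/64 = 12.5% or 8/48 = 16.7%.

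**What the Last Visit row leaves open.** Now drop the assumption that Baseline abnormality persists. If r of the 16 recover and n of the 64 are newly abnormal at the last visit, the row shows 16 − r + n. A row of 24 means n = 8 + r. With r from 0 to 16, n runs from 8 to 24, that is from 12.5% to 37.5% of 64. The planned Baseline and Last Visit rows would look the same throughout.

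**The case against.** The strongest reply is that the information largely exists elsewhere.

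- **Last Visit row.** SAP 3.2.5 applies by default, and SAP 10.4.4.3 does not exclude it, although it does not repeat it as the laboratory, vital sign and ECG sections do. A subject withdrawn while still abnormal therefore stays visible. This stands, but the row shows the last value and not the worst, and it combines old and new abnormality.
- **Adverse events.** SAP 10.2 defines TEAEs as events that are new or worse after first dose and tabulates them by period, intensity, seriousness and discontinuation. An event that leads to psychiatric admission would be a serious TEAE. This stands and limits the impact. It is not complete cover: Protocol 11.3.1, 11.3.4 and 11.3.5 say that clinically significant vital sign, physical and neurological findings are to be recorded as AEs, whereas Protocol 11.3.7 has no such rule. Mental status is part of the physical examination, so some findings would reach the AE tables that way.
- **Protocol commitment.** Protocol 13.4.1 promised only listings, so the SAP already does more. True, but once a table is planned it should measure the named variable.

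Two stronger readings are tempting. A reader might infer that subjects withdrawn under criterion 10 show up at one visit or not at all. The documents do not support that: the Last Visit row can carry them, withdrawn subjects are reassessed at Visits 8 and 9 (Protocol 8.3.2 and 8.4), and criterion 10 does not remove every abnormal result. A reader might also infer that unscheduled results are discarded, but they count towards the Last Visit.

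**Conclusion.** The point holds in a limited form. The named variable is a change, and the planned statistic is prevalence by visit. With or without the Last Visit row, no table of this assessment separates new or worsened abnormality from abnormality present at Baseline. Transient findings at unscheduled visits can be missed, and the EDV rule for this assessment is unstated.

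The size cannot be taken from the documents. The illustration shows the mechanism and rests on assumed counts; the documents give neither a Baseline rate of abnormality nor an onset rate. It does not support any fixed factor of understatement. A test statistic would also be out of place, since the summary is descriptive and no hypothesis test is planned for it.

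The consequence is a gap in reporting one safety variable. It does not mean that psychiatric harm would go unreported: the TEAE tables and subject listings remain.

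**What to change.** In SAP 10.4.4.3, by treatment group and for each item of the assessment:

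1. Add a shift table from Baseline to worst Treatment Period result, with the categories normal, abnormal but not clinically significant, and clinically significant. Use scheduled, unscheduled and EDV assessments.
2. Add the number and percentage of subjects not abnormal at Baseline who become abnormal at any time in the Treatment Period. Give the same for clinically significant abnormality, with the denominator restricted to subjects free of it at Baseline.
3. State in SAP 3.2.4 or 10.4.4.3 whether this assessment is mapped when done at an EDV, and confirm that the Last Visit row applies.

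The cost is a few lines of SAP text and one or two descriptive tables. No new data are needed, and no efficacy analysis or error rate is affected.

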#### 10.4.4.4 The Columbia-Suicide Severity Rating Scale (C-SSRS)

The C-SSRS questionnaire is self-administered by the subject and assessed by trained study personnel. This scale is used to assess suicidal ideation and behavior at Baseline (Visit 1), and at each subsequent study visit. C-SSRS data will be provided in subject listing for subjects with suicidal ideation and suicide behavior.

#### 10.4.4.5 Clinical Institute Withdrawal Assessment-Benzodiazepines (CIWA-B)

Subjects not entering the open label extension study (OLE) are tapered off study medication after completing the Maintenance Period (or if discontinued from the study). As part of monitoring of subjects for withdrawal symptoms during the Taper Period, the CIWA-B evaluation is performed at the end of the Maintenance Period (Visit 7), at the end of the Taper Period (Visit 8), and at the Safety follow-up visit (Visit 9). The CIWA-B questionnaire contains 22 questions, which are utilized to determine the type and the severity of withdrawal symptoms, ranging from mild, moderate, severe and very severe withdrawal symptoms (Busto et al, 1989). Subscores of each of the first 20 questions (scores from 0-4) are summed up to a total score:

Total score	Interpretation
1-20	Mild withdrawal
21-40	Moderate withdrawal
41-60	Severe withdrawal
61-80	Very severe withdrawal

In case of a missing subscore the total score is set to missing. The remaining two items of the 22 ask for sleeping duration and time to fall asleep. A by-subject listing will be provided, presenting the response values to all assessment parameters as well as the CIWA-B scores. In addition, a descriptive summary table will be prepared for total CIWA-B scores at scheduled visits.

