4.2.2 Other safety variables

Other safety variables are as follows:

- Incidence of TEAEs reported by the subject and/or caregiver or observed by the Investigator during the following periods: 16-week Treatment Period, 12-week Maintenance Period, 4-week Titration/Stabilization Period, and 3-week Taper Period
- Number of and reason for subjects requiring premature tapering due to TEAEs
- Number of and reason for subjects requiring a dose reduction during the Stabilization Period due to TEAEs
- Incidence of treatment-emergent SAEs during the following periods: 16-week Treatment Period, 12-week Maintenance Period, 4-week Titration/Stabilization Period
- Changes in clinical laboratory test parameters (including hematology, blood chemistry, and urinalysis)
- Changes in vital sign parameters (including pulse rate, systolic BP, diastolic BP, and respiratory rate)
- Changes in 12-lead ECG parameters
- Physical examination (including body weight) and neurological examination findings
- Changes in Psychiatric and Mental Status
- Occurrence of valvular abnormalities or pericardial effusion changes or other significant abnormalities as identified by 2-dimensional Doppler echocardiogram at each assessment by central reader
- Changes in withdrawal symptoms using Clinical Institute Withdrawal Assessment-Benzodiazepines (CIWA-B) from the End of Treatment Visit (Visit 7) to end of the Taper Period (Visit 8) and end of the SFU Period (Visit 9 [30 days after the last IMP intake]).

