At Visit 4 (at the end of the Stabilization Period), subjects will enter a 12-week Maintenance Period during which they will receive their target dose (or their fallback dose, if applicable). During the entire 12-week Maintenance Period, the dose of IMP (target dose or fallback dose) and concomitant AEDs must remain stable. Subjects must return to the clinic for scheduled visits as outlined in [Table 5-1](#).

Subjects who complete the Maintenance Period will return for an End of Treatment Visit. Subjects who discontinue early from the study will return for an Early Discontinuation Visit (EDV). Subjects completing the Maintenance Period will have the opportunity to enroll into the OLE study, EP0093. They will be converted to the entry dose of the EP0093 study, 400mg/day. Subjects withdrawing from the study or deciding not to participate in the OLE study (EP0093) will be progressively tapered off the IMP.

For subjects discontinuing the study:

Taper Period (4 weeks)

The 4-week Taper Period will be required for subjects who choose not to enroll in the OLE study or who discontinue prior to the end of the Maintenance Period. Subjects participating in the 4-week Taper Period should be gradually tapered off the IMP over a 3-week period (Table 7-3) followed by 1-week drug-free period. A faster or slower taper schedule than the suggested 3 weeks may be implemented, if medically necessary, as per the Investigator's medical judgement. Subjects will start their taper at the EDV/End-of-Treatment (Visit 7) and will return 1 week after last intake of IMP for the End-of-Taper Visit at Visit 8. Changes to concomitant AED(s) are not allowed during the taper of PSL unless they are medically necessary as per the Investigator's medical judgement to treat rebound seizures.

Safety Follow-Up Period

Safety follow up for subjects not entering the OLE will consist of 1 required visit, 30 days after the last IMP intake (Week 23 or sooner in case of early discontinuation) including an echocardiogram. An additional follow-up echocardiogram will be performed at 6 months (± 1 month) after the last IMP intake only for subjects exposed to IMP for more than 3 weeks.

For subjects continuing to the OLE study:

Conversion Period (3 weeks)

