7.2.2 Taper Period

The Taper Period, in case of withdrawal or completion of the study, will comprise 3 weeks as presented in Table 7-3. A faster or slower taper schedule than the suggested 3 weeks may be implemented if medically necessary, as per the Investigator's medical judgment. During the Taper Period, the dose of PSL must always be administered as bid morning and evening doses, approximately 12 hours apart. Concomitant AED dosages should be kept stable throughout the entire study including the Taper Period.

Subjects should be monitored during the Taper Period for withdrawal symptoms, including behavioral changes, withdrawal-related AEs or rebound seizures as well as the severity of the CIWA-B withdrawal scores. Withdrawal symptoms may require medical treatment for management of severe withdrawal symptoms. Additional AEDs (excluding prohibited medications) may be added and/or changes to dose regimens of concomitant AEDs are permitted if medically necessary as per Investigator's medical judgement to manage rebound seizures.

Table 7-3: Taper Period dosing

Dose Arm	Dose in mg per intake (morning-evening) during taper ^a				
	Week 16	Week 17		Week 18	
PSL 800mg/day	300-300	200-200	150-150	100-100	50-50
PSL 600mg/day					
PSL 400mg/day	200-200				
PSL 300mg/day	150-150	100-100		50-50	
PSL 200mg/day	100-100				
PSL 150mg/day	75-75				
PSL 100mg/day	50-50				
PSL 50mg/day	25-25				
Placebo	1-1				

PSL=padsevonil

^a Taper Period for subjects who choose an early discontinuation may occur before Week 16.

Note: Taper steps may vary in length by ±3 days per week.

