13.4 Planned safety and other analyses

13.4.1 Safety analyses

Adverse events will be coded using the Medical Dictionary for Regulatory Activities (MedDRA[®]). Adverse events will be summarized by MedDRA system organ class and preferred term. The incidence of SAEs, AEs leading to premature discontinuation or dose tapering, and related AEs, and the incidence of AEs by maximum intensity, will also be summarized.

Laboratory values, ECG data (ventricular rate, PR, QTcB, QTcF, and QRS) and arrhythmias, vital signs, weight, and changes from Baseline in these measures will be summarized by period, visit, and treatment group. Possibly clinically significant treatment emergent abnormalities for laboratory values, vital signs, and weight will be listed and summarized by period and visit for each treatment group.

Electrocardiogram abnormalities as well as physical and neurological abnormalities will also be listed by period and visit. Quantitative safety parameters will be summarized descriptively by time point and treatment group. Categorical safety summaries will provide the number and percentage of subjects within each summarized category.

Doppler echocardiogram results at Baseline and during and after treatment, and changes from Baseline, will be listed and descriptively summarized.

All C-SSRS data obtained at Baseline and subsequent visits will be reported as a listing ordered by subject and visit. Psychiatric and Mental Status assessment and CIWA-B data will also be included using listings.

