### **8.3.2.23 Change from baseline in seizure frequency**

The 28-day adjusted seizure frequency and change from baseline will be summarized descriptively by the treatment group in Titration and Stabilization, Maintenance, and Treatment Periods for observable focal-onset seizures and Type I seizures. The imputation rule described in Section 4.2.1 will be applied.

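### The planned CIWA-B table shows total scores at nominal visits, not the pre-specified within-subject change from the start of taper, and its rows hold different subjects

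*SAP*

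**What the plan says.** Protocol section 4.2.2 lists, among the other safety variables, "Changes in withdrawal symptoms using Clinical Institute Withdrawal Assessment-Benzodiazepines (CIWA-B) from the End of Treatment Visit (Visit 7) to end of the Taper Period" and then to the safety follow-up visit. SAP section 2.4.2 repeats the definition: "from the End of Treatment Visit (Visit 7) to end of the Taper Period (Visit 8) and end of the SFU Period". The variable is a change, and its reference is the score at the start of taper.

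Two groups taper: completers who decline the open-label extension (OLE), and subjects who stop early. Protocol section 5.1 gives the starting point: "Subjects will start their taper at the EDV/End-of-Treatment (Visit 7) and will return 1 week after last intake of IMP". Protocol section 8.2.3.3, which covers both Visit 7 and the earlier EDV, has CIWA-B completed there by subjects who are tapering.

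For the analysis, Protocol section 13.4.1 says "Psychiatric and Mental Status assessment and CIWA-B data will also be included using listings". SAP section 10.4.4.5 goes further. It plans a by-subject listing and then "In addition, a descriptive summary table will be prepared for total CIWA-B scores at scheduled visits". SAP section 3.2.4 sets the rule for early discontinuation: in-clinic safety assessments are moved to the next scheduled visit, but "All other assessments (such as questionnaire and PK samples) collected on an EDV will not be mapped".

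**The concern.** The table is cross-sectional while the variable is longitudinal, and the plan never states which score is the reference. A reader will naturally compare the Visit 7 row with the Visit 8 and Visit 9 rows, and those rows are not made up of the same people. If early discontinuers start the taper with higher scores than completers, their arrival at Visit 8 looks like a withdrawal effect. If they start lower, a real effect can be hidden. Early discontinuation may also differ by dose, so the distortion need not be equal across arms. Padsevonil binds at the benzodiazepine site, and CIWA-B is the instrument chosen to look for withdrawal.

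**Working it through.** **1. Is a change planned anywhere for CIWA-B?** No. SAP section 10.4.4.5 mentions only item responses and total scores. Elsewhere the SAP asks for change from Baseline explicitly: HADS (8.3.2.21), QOLIE-31-P (8.3.2.20), laboratory (10.3), vital signs (10.4.1) and ECG (10.4.2).

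**2. Does a general rule supply the reference?** No. SAP section 3.3.2 takes the last value before first dose. The schedule of assessments first collects CIWA-B at Visit 7/EDV, so no such value exists.

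**3. Who is in each row?** CIWA-B is described as a questionnaire (Protocol section 11.3.8, SAP section 10.4.4.5), so the no-mapping rule in SAP section 3.2.4 covers it.

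- Visit 7: completers who taper.
- Visits 8 and 9: those completers plus early discontinuers who attend.
- EDV scores: listed under the EDV. The Treatment Period ends on the EDV date (SAP 3.2.2.2), so the default Last Visit row (SAP 3.2.5) could pick them up, as an unpaired value. SAP section 10.4.4.5 does not name that row, whereas the SSG, QOLIE-31-P and HADS sections do.

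**4. What does a change of mix do?** Let p be the share of early discontinuers among those scored at Visit 8, and D their mean start-of-taper score minus that of completers. If nobody changes, the apparent shift from Visit 7 to Visit 8 is p × D. The scores below are invented; the scale runs from 0 to 80 (20 items scored 0 to 4).

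- False signal: completers 10, early discontinuers 20, p = 0.5, no change in anyone. Visit 7 shows 10; Visit 8 shows 0.5 × 10 + 0.5 × 20 = 15. Paired change is 0.
- Hidden signal: completers 20, early discontinuers 10, p = 0.5, everyone rises by 5. Visit 7 shows 20; Visit 8 shows 0.5 × 25 + 0.5 × 15 = 20. Paired change is 5.

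**5. How large could p be?** With d the early discontinuation rate and u the OLE uptake among completers, and assuming every early discontinuer tapers and attends:

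p = d / (d + (1 − d)(1 − u))

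Neither d nor u is given for this trial. The only uptake figure is from the proof-of-concept study, 42/55 = 76.4% (Protocol section 2.3.1). It counts all exposed subjects, not completers, so using it for u is itself an assumption.

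| d | u = 70% | u = 76.4% | u = 90% | u = 95% |
|---|---|---|---|---|
| 5% | 14.9% | 18.2% | 34.5% | 51.3% |
| 10% | 27.0% | 32.0% | 52.6% | 69.0% |
| 20% | 45.5% | 51.4% | 71.4% | 83.3% |
| 30% | 58.8% | 64.5% | 81.1% | 89.6% |

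Early discontinuers are a majority only when u exceeds 1 − d/(1 − d): 94.7% at d = 5%, 88.9% at 10%, 75.0% at 20% and 57.1% at 30%.

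**6. Can it differ by arm?** Take D = 10, nobody changing, and two arms with p = 27.0% and 51.4%. The apparent shifts are 2.7 and 5.1 points, a difference of 2.4 that owes nothing to withdrawal.

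**7. Taper after conversion.** SAP Table 3-1 allows taper to begin after Visit 8. Protocol sections 8.2.3.3 and 8.3.2 collect CIWA-B at Visits 7 and 8 only from subjects tapering, so these subjects may have no start-of-taper score.

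**The case against.** The best defence is that the SAP already exceeds the protocol, which plans only listings for CIWA-B. The EDV score is in the listing, SAP section 3.1 says listings carry calculated values where applicable, and a reader could work out each subject's change. The Last Visit rule may bring EDV scores into the table. Placebo subjects taper too, so a concurrent comparison exists, and the severity bands give an absolute reading. This is also a descriptive variable in the lower safety tier.

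The low tier stands and limits the weight of the point. The rest does not close the gap. Protocol section 13.2 promises summary statistics for all safety variables, and this one is a change. A Last Visit mean is not paired with anything. If change is taken from listings, the reference is chosen after the data are seen. The comparison with placebo helps only if the mix of completers and early discontinuers is similar across arms. The bands are wide: every score from 1 to 20 is mild.

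It could also be said that the EDV simply is Visit 7, since the schedule shares a column. SAP section 3.2.4 treats it otherwise, as a visit without a window that maps, where it maps at all, to the next scheduled visit.

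Three stronger readings are tempting, and the documents do not support them.

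- **Early discontinuers have no baseline.** They do: CIWA-B is collected at the EDV, where their taper starts, and is listed. What is missing is a rule that uses it.
- **Early discontinuers are most of those who taper.** This depends wholly on assumed rates, as the table shows.
- **Rebound seizures are neglected in the same way.** Protocol section 7.2.2 does say "Subjects should be monitored during the Taper Period for withdrawal symptoms, including behavioral changes, withdrawal-related AEs or rebound seizures", and SAP section 8.3.2.23 has seizure frequency "summarized descriptively by the treatment group in Titration and Stabilization, Maintenance, and Treatment Periods" only. But no taper-period seizure variable is pre-specified. Clinically significant worsening is recorded as an adverse event (Protocol section 11.1.1.1) and tabulated for the Taper and Safety Follow-up Period (SAP section 10.2). A frequency table would also collide with the last-dose cut-off in SAP section 8.

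**Conclusion.** The point holds. Followed as written, the SAP does not tabulate the withdrawal variable that both documents define, and the table it does plan invites a comparison between rows with different membership. The bias equals p × D when nobody changes. Its direction depends on the sign of D, and neither quantity can be established from the documents. The 15% to 90% range for p rests on assumed dropout of 5% to 30% and completer uptake of 70% to 95%, with all early discontinuers tapering and attending. The defect needs no majority: any p above zero makes the rows differ in membership.

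The conclusion rests on reading the scheduled-visit wording and the no-mapping rule literally. It affects a descriptive safety table, not the efficacy results or the primary safety variables. It is worth correcting because the data to do it properly are already collected.

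**What to change.** In SAP section 10.4.4.5:

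- Define the CIWA-B reference as the total score at Visit 7 or at the EDV, whichever starts the subject's taper.
- Tabulate within-subject change from that reference to Visit 8 and to Visit 9 by treatment group, giving the number of pairs, and show completers and early discontinuers separately as well as together.
- State how subjects who taper after conversion are handled, for example listed but left out of the paired table when no start-of-taper score exists.

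In SAP section 3.2.4, exempt CIWA-B from the no-mapping rule for this purpose.

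The cost is a few lines of SAP text and one descriptive table. No visit, assessment or data item is added.
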